### 7.6.2 Participant Reported Outcomes (PRO) Assessment

*(Translations Not Available; enrollment restricted to English-speaking participants)*

#### EORTC Quality of Life Questionnaire-Core 30/Brain Cancer Module-20 (EORTCQLQ-30/BN20)

The EORTC QLQ-C30/BN20 were developed and validated for use in this patient population. The QLQ-C30 is a 30-item self-report questionnaire that has patients rate the items on a 4-point scale, with 1 “not at all” to 4 “very much.” The instrument measures several domains, including physical functioning, role functioning, emotional functioning, cognitive functioning, social functioning, fatigue, pain, nausea and vomiting, and several single items (dyspnea, insomnia, anorexia, constipation, diarrhea, and financial impact). The BN20 consists of 4 scales comprised multiple items (future uncertainty, visual disorder, motor dysfunction, communication deficit) and 7 single items (headache, seizures, drowsiness, hair loss, itching, difficulty with bladder control, and weakness of both legs). The combined instrument takes an average of 8 minutes to complete by patients with primary brain tumors.

### 7.6.3 Neurocognitive Function Assessments

*(Translations Not Available; enrollment restricted to English-speaking participants)*

The healthcare professional who is responsible for test administration in this study must be pre-certified by WF NCORP Site Coordinator for each test, unless they are currently certified with WF NCORP for each test. Refer to Section 7.6.1.

The tests in the neurocognitive test battery were selected because they are widely used standardized psychometric instruments that have been shown to be sensitive to the impact of cancer and the neurotoxic effects of cancer treatment in other clinical trials. The tests have published normative data that takes into account age, and where appropriate, education and gender. The tests are given by certified site administrators, and the total time for the cognitive assessment is approximately 38 minutes, as follows:

Cognitive Domain	Test	Administration Time (minutes)
Memory	Hopkins Verbal Learning Test-Revised (HVLTR)	5
Cognitive Processing Speed	Trail Making Test, Part A	3
Executive Function	Trail Making Test, Part B	5
Verbal fluency	Controlled Oral Word Association Test (COWAT)	5
Cognitive Reserve	Shipley Institute of Living Scale	20

#### Hopkins Verbal Learning Test-Revised (HVLTR)

The patient is asked to recall a list of 12 words over three trials. After a delay of 20 minutes, the patient is asked to spontaneously recall the words. The patient is then asked to identify the list words from distractors. There are six alternate forms of this test to minimize practice effects. The test measures learning memory retrieval, and memory consolidation processes. This measure has been widely used in clinical trials.

#### Trail Making Test, Part A

This is a test of visual-motor cognitive processing speed, requiring the patient to connect dots in numerical order from 1 to 25 as fast as possible.

#### Trail Making Test, Part B

This test is similar to Trail Making Test Part A, with the additional requirement of shifting mental set (an executive function). The patient connects dots alternating numbers and letters as fast as possible.

#### Controlled Oral Word Association Test (COWAT)

This is a test of phonemic verbal fluency. The patient is asked to produce as many words as possible in 60 seconds beginning with a specified letter. There are two alternate forms of this test.

#### Shipley Institute of Living Scale-Version 2 Vocabulary

This vocabulary test requires respondents to read a target word and select one of four words that most closely means the same thing. Score it total correct of 40 items. This provides an assessment of premorbid intellectual functioning comparable to a verbal IQ and thus is a proxy for cognitive reserve. It will be administered only at baseline.

## 8. CRITERIA FOR EVALUATION AND ENDPOINT DEFINITION

### 8.1 Primary Endpoints

**Retention rate at 10 weeks of treatment (6 weeks during RT and 4 weeks [1 month] post RT):**

Retention will be defined as compliance with drug therapy for at least 75% of doses during the 10 week treatment and completion of the composite neurocognitive battery as detailed below.

**Neurocognitive performance measured by the Clinical Trial Battery Composite (CTB COMP) score at 10 weeks of treatment (6 weeks during RT and 4 week [1 month] post RT):** Tests have been selected to represent a range of functions affected by cancer and RT including attention, memory, working memory, executive functions and verbal fluency. All cognitive testing will be performed by trained and certified research staff. Proposed neurocognitive measures are: Hopkins Verbal Learning Test-Revised (HVLT-R Delayed Recall; 5 min); Trail Making Test A & B (TMT; 8 min) and Controlled Oral Word Association test (COWAT 3 letters; 5 min). The composite neurocognitive score is defined as the arithmetic mean of the standardized scores from the HVLT-R total recall, HVLT-R Delayed Recall, HVLT-R Delayed Recognition Discriminability (all portions of the HVLT-R delayed recall), Trail Making Test Part A, Trail Making Test Part B, and COWAT. We will assess the effect size in terms of the composite neurocognitive score.

The entire battery of neurocognitive tests and questionnaires will take approximately 38 minutes to complete. We have used a similar battery successfully in two phase 2 studies and one phase 3 study involving breast and brain tumor cancer survivors. Data completeness in those studies was over 95%.

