Study hypotheses that will be explored include the following: 1) patient retention will be sufficiently high to proceed forward with a randomized trial of Ramipril; 2) patients receiving Ramipril will have better neurocognitive function (assessed using the Clinical Trial Battery Composite Score) compared to historical controls who did not receive Ramipril; 3) neurocognitive decline will be slower in patients receiving Ramipril; 4) patients receiving Ramipril will have better scores for the individual neurocognitive function tests; 5) patients receiving Ramipril will have better mood and quality of life and less fatigue and sleep disturbance.

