## **12.2 Accrual and Feasibility**

### **Sample Size**

We will assess the dropout rate to inform us regarding the design of a subsequent randomized study. We will test the null hypothesis that retention  $< 65\%$  versus the alternative hypothesis that retention  $\geq 65\%$ , with 90% power for detecting an alternative retention of 80%. The 65% threshold is related to retention rate, and is different from the 75% of doses required for compliance (Section 12.1). Assuming a 1-sided test at the 0.05 significance level, we obtain a sample size of 75 participants. The sample size calculation was conducted using NQuery Advisor v7.0. Based on this calculation, we will plan for a sample size of 75, which will allow us to determine with a high level confidence whether or not the retention rate is sufficient to justify a subsequent study to this pilot.

We will also estimate the effect size in terms of reduction in neurocognitive decline in the intervention group as compared to historical controls. No formal statistical hypothesis will be tested for the purpose of declaring efficacy. The effect size, along with the estimate of the dropout rate, will be used to power and assess the feasibility of a planned subsequent randomized study. We expect an accrual rate of approximately 4 per month based on prior NCORP studies in similar brain tumor populations.

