## **12.3 Primary Objective, Endpoint(s), Analysis Plan**

The primary objective of this study is to assess the retention rate of patients at 10 weeks of Ramipril treatment (6 weeks during RT and 4 weeks post RT) defined by compliance with drug therapy for at least 75% of doses during the 10 week period and completion of the composite neurocognitive battery. The retention rate will be estimated by count and percentage with corresponding 95% exact binomial confidence interval. All patients receiving at least one treatment of Ramipril will be evaluable for retention.

Additionally, the Clinical Trial Battery Composite Score is derived from the arithmetic mean of the standardized scores from the HVLt-R total recall, HVLt-R Delayed Recall, HVLt-R Delayed Recognition Discriminability, Trail Making Test Part A, Trail Making Test Part B, and COWA. For CTB COMP, the effect size of neurocognitive change of patients receiving Ramipril versus patients who do not receive Ramipril in patients with newly diagnosed GBM using the control arm of RTOG 0825 as the comparison group will be calculated with a corresponding 95% confidence interval.

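### The 10-week cognitive effect size is on the CTB COMP score in 8.1 but on change in 12.3, and neither change nor the standardising SD is defined, although this number is meant to power the next trial

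*Combined protocol and SAP*

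**What the plan says.** Section 8.1 (Primary Endpoints) names the second primary endpoint as performance on the "Clinical Trial Battery Composite (CTB COMP) score at 10 weeks of treatment" and states "We will assess the effect size in terms of the composite neurocognitive score". It mentions neither baseline nor change. Hypothesis 2 in 12.1 is also worded as a level: "patients receiving Ramipril will have better neurocognitive function (assessed using the Clinical Trial Battery Composite Score) compared to historical controls".

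Section 12.3 gives the analysis of CTB COMP as "the effect size of neurocognitive change of patients receiving Ramipril versus patients who do not receive Ramipril in patients with newly diagnosed GBM", with the control arm of RTOG 0825 as comparator and a 95% confidence interval. Section 12.2 (Sample Size) says "We will also estimate the effect size in terms of reduction in neurocognitive decline in the intervention group as compared to historical controls". That sentence does not name CTB COMP. The section adds that the effect size, together with the dropout estimate, "will be used to power and assess the feasibility of a planned subsequent randomized study". It also says that no formal test of efficacy is planned.

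Section 12.4 deals with the lack of randomisation by considering covariate adjustment, but for secondary analyses. Its pre-specified covariates are MGMT methylation, KPS and extent of resection; baseline CTB COMP is not listed. Section 12.5 proposes a mixed model without saying how the baseline score enters it.

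**The concern.** A week-10 score and a change from baseline are different quantities, and in this design they can differ in two ways.

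The first is the numerator. The comparison is with an external cohort, so mean baseline CTB COMP may differ between the two groups. A raw week-10 contrast contains that gap; a change contrast subtracts it.

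The second is the denominator. A standardised effect needs a stated SD. The plan could be carried out with the baseline SD, the week-10 SD or the SD of change, and one set of data then yields several effect sizes.

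Sizing the next trial is a declared use of this estimate. An analyst following 8.1 and one following 12.3 could pass different numbers to the designers of that trial, and the choice could be made after the data are seen.

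**Working it through.** **1. The plan's own sample size.** The only computed sample size is for retention (12.2: 65% against 80%, one-sided 0.05, 90% power).

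n = [1.645·√(0.65·0.35) + 1.2816·√(0.80·0.20)]² / 0.15² = 74.8, rounded up to 75.

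The exact binomial rule of at least 56 of 75 retained gives alpha 0.0485 and power 0.9003. So N = 75 reproduces, and nothing below affects it.

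**2. Inputs for the cognitive endpoint.** The documents give no SD of CTB COMP, no correlation r between baseline and week 10, and no target effect. I assume SD = 1 at both times, a difference of 0.30 SD for illustration, and r from 0.3 to 0.8.

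**3. Denominator, with equal baselines.** SD of change = SD·√(2(1−r)). If each effect is divided by its own SD, the ratio of change-scale to score-scale effect is 1/√(2(1−r)).

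The last two columns show what happens if a change-scale effect d is later used to size a trial analysed on the unadjusted week-10 score (80% power, two-sided 0.05):
- n per arm = 2·((1.96 + 0.8416)/d)²
- true power = Φ(0.30·√(n/2) − 1.96)

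The correct n for that score analysis is 175 per arm.

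| r | SD of change | Ratio | Change-scale d | n per arm from that d | True power on the score |
|---|---|---|---|---|---|
| 0.3 | 1.183 | 0.85 | 0.254 | 245 | 0.91 |
| 0.5 | 1.000 | 1.00 | 0.300 | 175 | 0.80 |
| 0.7 | 0.775 | 1.29 | 0.387 | 105 | 0.58 |
| 0.8 | 0.632 | 1.58 | 0.474 | 70 | 0.43 |

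At r = 0.5 the scales agree. Below it the direction reverses and the trial would be too large. If both effects were divided by the same SD, the ratio would be 1 throughout.

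**4. Numerator, with unequal baselines.** Let g be the baseline gap (ramipril minus control) and let the difference in change be 0.30 SD.
- Raw week-10 contrast = 0.30 + g.
- Change contrast = 0.30.
- Contrast adjusted for baseline = (0.30 + g) − r·g, because the within-cohort slope equals r when the variances are equal.

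| g (SD) | Raw week-10 contrast | n per arm from it | Change contrast | Adjusted contrast, r = 0.7 |
|---|---|---|---|---|
| −0.2 | 0.10 | 1570 | 0.30 | 0.24 |
| 0 | 0.30 | 175 | 0.30 | 0.30 |
| +0.2 | 0.50 | 63 | 0.30 | 0.36 |

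The movement in the raw contrast does not depend on r or on the choice of standardiser.

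**The case against.** The best defence is that 12.2 and 12.3 are the analysis sections and both lean to change. Section 8.1 may only be naming the instrument and the time point, and its effect-size sentence could cover change in the composite. Hypothesis 2 is a general statement, and hypothesis 3 beside it speaks of slower decline. On that reading the planning number is on the change scale throughout.

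Much of this stands. The effect-size sentence in 8.1 is not decisive alone; the conflict rests on the endpoint being defined there as the score at 10 weeks, read against 12.3. But even if 12.3 governs, change is undefined (simple difference or baseline-adjusted) and the standardiser is unnamed.

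A reader might infer that the two sections must give different effect sizes, that the change-scale effect is the larger, or that the next trial will be underpowered. The documents support none of these. They do not give r, and the scales coincide at r = 0.5 with equal baselines. They do not say the effect will be divided by the SD of change: CTB COMP already averages standardised scores, so a difference in those units fits the text equally well. No section plans to apply a change-scale effect to an unadjusted score endpoint, which is the step that produces the power loss in the first table.

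It is also fair that the stakes are limited: no efficacy claim rests on this estimate.

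**Conclusion.** The inconsistency is real and concerns a primary endpoint: 8.1 puts the effect size on the score, 12.3 puts it on change, and neither change nor the standardising SD is defined. The firmest consequence is the baseline gap. Followed literally, 8.1 lets any difference in baseline score between non-randomised cohorts pass one-for-one into the effect. In the illustration, gaps of ±0.2 SD move it from 0.10 to 0.50.

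The scale ratio (0.85 to 1.58 for r from 0.3 to 0.8) is conditional on equal variances, equal baselines and each effect being divided by its own SD. Its size and direction cannot be settled from the documents. Mis-sizing follows only if the effect is later used on a scale other than that of the new trial's analysis. The pilot's retention decision is untouched.

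**What to change.** Align 8.1, 12.2 and 12.3 on one estimand: the difference in week-10 CTB COMP, ramipril minus RTOG 0825 control, adjusted for baseline CTB COMP. Report it in z-score units with a 95% confidence interval, and name the standardiser for any effect size; the pooled baseline SD is suitable because treatment cannot affect it.

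Report the simple change-from-baseline contrast as a sensitivity analysis. Without randomisation the two can differ, as the second table shows, and neither removes confounding by itself.

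Also report the baseline, week-10, change and residual SDs and the baseline-to-week-10 correlation, so that the next trial can be sized for whichever analysis it adopts.

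The cost is SAP wording and a little extra analysis. Baseline and week-10 testing are already in the schedule (7.1), and 2.3 records agreed access to the RTOG 0825 data. I assume those data include individual baseline and week-10 scores.

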### 8.2 Secondary Endpoints

**Participant reported outcomes (PRO):** Participant-reported outcomes will complement the neurocognitive battery. The EORTC Quality of Life Questionnaire-Core 30/Brain Cancer Module-20 (EORTCQLQ30/BN20) will measure several domains of functioning (physical, emotional, cognitive, social, fatigue, pain, etc.) (8 minutes). Each cognitive test and PRO proposed has adequate psychometric properties and has been used previously in clinical trials of oncology patients.

**Imaging:** Adequate imaging for diagnostic, treatment planning and follow-up imaging will follow standard of care practices and will include contrast-enhanced T1-weighted MRI and T2 or FLAIR imaging. Contrast-enhanced CT will be allowed only in cases where patients are unable to undergo MRI because of non-compatible devices. MRI of the brain will be performed 1- and 4-month post-RT or until time of tumor progression, should that occur prior to the 4-month post-RT time point. Response assessment will be based on treating investigator assessment and institutional standard of care. Imaging parameters will only be utilized to measure response and progression.

**Other variables to be measured:** Sociodemographic variables to be assessed in a questionnaire at baseline will include age, education, race/ethnicity, menopausal status, co-morbid medical conditions, concomitant medication, marital status, socioeconomic status, tumor size and location. Variables to be assessed after completion of each treatment phase by treating physician include dates, dose and compliance of temozolomide administration, radiation dose, radiation dose per fraction, and radiation volume (e.g. planned treatment volume (PTV)). *Cognitive reserve* (CR) will be measured with the Shipley Scale-Vocabulary with educational (years in school) and occupational attainment (standardized 8-level classification) also measured as proxies for CR.

**Biomarkers:** APOE genotype, a risk factor for cognitive impairment and dementia, will be derived from

whole blood samples taken at baseline at the site of study enrollment. See Section 10.1 for sampling handling and processing.

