### 1.2 Secondary Objectives

- 1.2.1 To estimate the time to neurocognitive decline with GBM receiving chemoradiotherapy and Ramipril. Decline will be defined as the time at which a change greater than the reliable change index for any of the individual cognitive tests is experienced for a particular patient.
- 1.2.2 To estimate the effect of treatment with Ramipril on and variability of specific non-memory cognitive functions including attention, executive function, visuo-motor skills, working memory, a screening measure of global cognitive function, mood, quality of life, fatigue and sleep disturbance.
- 1.2.3 To collect preliminary data on the presence of apolipoprotein epsilon (ApoE) isoform 4 serum (peripheral blood lymphocyte) test positivity as measured by quantitative PCR.
- 1.2.4 To estimate neurocognitive function in surviving patients at the 4 month post RT endpoint.
- 1.2.5 To estimate response as reported by treating physician assessments.

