- (2) Negative serum or urine pregnancy test required within 14 days prior to enrollment for women of childbearing potential. Results may be used from routine local lab.
- (3) MRI/CT Brain scans at the indicated time points are considered standard of care per national guidelines. As per section 4.1.7, all available brain MRI or CT imaging reports from surgery to study completion must be submitted. This includes any post-operative or pre-radiation scan reports. Treating physician assessment of tumor response – i.e. response, progression or stable disease – will be captured for each completed imaging study.

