MRI/CT Brain: MRI Brain will be completed per standard of care at each study site. Sites are asked to provide MRI final reports with the specific visit form. As per section 4.1.7, patients who are unable to undergo MRI scanning should have CT brain scans done as per this schedule. Treating physician assessment of tumor response – i.e. response, progression or stable disease – will be captured for each completed imaging study.

Toxicity Assessments: Assessments by the study team will be done from Week 1 of RT and the start of Ramipril to 5-month post RT (end of study). This time period includes 30 days after treatment with Ramipril. Refer to section 6.2 for reported adverse events and risks when taking Ramipril.

Adverse Event Reporting: Refer to Section 10 of the protocol for specifics.

**Medication Diary:** Each patient is asked to fill in a Ramipril Medication diary and return it to the study team weekly during radiation therapy (weeks 1-6), and monthly on 1- and 4- month post RT visit. Since 2- and 3- month visits can be phone calls, the patient will need to mail back these diaries to the study team. Refer to Appendix D for a Ramipril Medication diary.

**Pill Count:** Patients will be asked to bring pill bottles to visit. Study team will count and record pills given, remaining and taken on the visit CRF.

**Ramipril Administration:** This study drug will be provided at no charge to patients for oral administration daily from Week 1 RT to post 4-month RT (Week 22). Study team will be required to order, distribute and inventory study drug. Refer to Sections 6.3 – 6.8 and for titration schedule 5.1.2 for details.

**Chemoradiation Summary:** At the RT Completion (Week 6) visit, a summary of the standard of care chemotherapy and radiation therapy will be gathered.

**Off Agent:** Use this form when a patient goes Off Agent either at the completion of study drug administration per protocol or at the time of early discontinuation. All study assessment should be continue to be completed, unless the patient is unwilling or withdraws consent. LabCorp samples do not need to be collected after the patient is Off Agent. Please use local labs to complete assessment information in REDCap.

**Off Study:** Use this form when a patient goes Off Study by either withdrawing consent or completing the study. This form serves as a way to track the patient status.

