#### 8.3.1 Off-Agent Criteria

Participants may stop taking study agent for one or more of the following reasons: completed the protocol-prescribed intervention, adverse event (AE) or serious adverse event (SAE), inadequate agent supply, refusal to continue with study procedures, the need for contraindicated concomitant medications, medical contraindication, disease progression, death or treating physician decision.

Date and reason off-agent should be documented on the Off Agent case report form. Reasons that are not specified on the form should be coded as 'Other' and a brief description provided. Patients who go off-agent must be followed for adverse events (AEs) for at least 30 days from their last treatment.

Note that participants who go off-agent should be encouraged to stay in the study and provide data at the regularly scheduled visits. Local NCORP site staff should complete the study assessment with the patient, especially the neurocognitive and PROs testing and toxicity assessments. LabCorp samples do not need to be collected once the patient is "Off Agent.". Local institutional labs can be used to assess the participant after they are off Ramipril.

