Treating physician response rate will be summarized at each timepoint with corresponding 95% confidence intervals. Time to neurocognitive failure will largely follow the method reported in Gilbert *et al.* for evaluating if there is meaningful difference in the risk of cognitive progression. Neurocognitive failure will be defined as the first decline on reliable change index on any of the individual cognitive tests. In the presence of competing risks for neurocognitive failure, including GBM-related mortality risk, we plan to explore the use of competing risks methods for both descriptive statistics (e.g. the Kaplan-Meier curves) and competing risk regression analysis. Competing risk methods are needed because time to neurocognitive failure is not independent of mortality and ignoring events from competing risk will lead to biased results. The competing risk analysis will be based on the method proposed in Gray and Fine and Gray using SAS macro %CIF and PROC PHREG. Patient reported outcomes will be assessed as described above for the CTB COMP.

Exploratory subgroup analyses will be conducted for all 4 month post RT outcomes by whether the patient received Optune® (also known as Tumor-Treating Fields or TTFIELDS) as part of their standard treatment following RT. Differences by Optune® for continuous outcomes will be assessed by two-sample t-tests where parametric assumptions hold; otherwise Mann-Whitney U tests will be applied. For categorical outcomes, Fisher's exact or Chi-square tests will be implemented. Corresponding 95% confidence intervals will also be presented for outcomes within each subgroup.

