## **12.7 Evaluation of Toxicity**

### **Evaluation of Toxicity and Adverse Effects of Ramipril**

All patients will be evaluable for toxicity from the time of their first treatment with Ramipril. Toxicities will be quantified using the CTCAE v5.0 for Toxicity and Adverse Event Reporting. Fisher exact tests will be used to assess treatment differences in the incidence of individual toxicities, and logistic regression will be used to assess treatment differences in the incidence of any grade 3 or higher toxicity possibly, probably or likely related to Ramipril adjusting for baseline patient characteristics. In order to rule out cytoprotection of tumor by Ramipril, response rates will be compared to historical controls from RTOG 0825.

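### The only planned check for tumour protection by Ramipril is a response rate, which on its ordinary reading cannot see a shift from stable disease to progression; progression and death are collected but not analysed for this purpose

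*Combined protocol and SAP*

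**What the plan says.** Section 12.7 names one analysis for the tumour question: "In order to rule out cytoprotection of tumor by Ramipril, response rates will be compared to historical controls from RTOG 0825". It gives no timepoint, denominator, test or margin. Section 12.4 adds one descriptive summary: "Treating physician response rate will be summarized at each timepoint with corresponding 95% confidence intervals". Objective 1.2.5 is worded to match: "To estimate response as reported by treating physician assessments".

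The data collection is wider than this. Section 8.2 (Imaging) says "Imaging parameters will only be utilized to measure response and progression" and sets the schedule: "MRI of the brain will be performed 1- and 4-month post-RT or until time of tumor progression". Footnote 3 to the Schedule of Events in Section 7.1 says that the treating physician's assessment, "response, progression or stable disease – will be captured for each completed imaging study", and Section 7.3 repeats the three categories. Section 8.3.1 includes "disease progression, death or treating physician decision" among the reasons for stopping study agent, with date and reason recorded. Section 8.3.2 lists progression and death as off-study reasons. Section 10.3 requires all grade 5 events to be reported.

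In Section 12, death appears only as a competing risk for neurocognitive failure. There is no progression proportion, time to progression, progression-free survival or overall survival.

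**The concern.** Ramipril is given throughout chemoradiation because it may protect irradiated tissue. The plan therefore asks, rightly, whether it also protects tumour. If it did, the harm could appear as more or earlier progression or death. A response rate in its ordinary sense divides patients into responders and all others. A patient who progresses instead of remaining stable stays in the same group, and the rate says nothing about when progression occurred.

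Eligibility may sharpen this. Section 4.1.1 requires partial or gross total resection, so some patients may have little residual tumour in which a response could be seen, although they can still progress or die. The documents do not say how many.

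At stake is the reliability of a reassuring statement about tumour control in the report of a pilot that is meant to inform a randomised trial.

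**Working it through.** **The plan's own figure.** The tumour check has none: no expected rate, margin or control-arm size is given. The only sized quantity is retention (Section 12.2: 65% against 80%, one-sided 0.05, power 0.90):

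n = [(1.645·√(0.65·0.35) + 1.282·√(0.80·0.20)) / 0.15]² = 74.8, so 75.

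This reproduces. It supplies the 75 patients used below and has no other bearing on the point.

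**What is collected and what is analysed**

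| Item | Collected | Analysed for tumour protection |
|---|---|---|
| Response | each completed scan (7.1, 7.3) | yes (12.7; summarised in 12.4) |
| Stable disease | each completed scan | no separate analysis |
| Progression | each completed scan; off-agent and off-study reason | none |
| Death | grade 5 reporting; off-agent and off-study reason | none |

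All rates and control sizes below are assumptions, because the documents give none. n₀ is the number of controls.

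**Case 1: a pure shift from stable disease to progression or death.** Controls: 15% response, 55% stable, 30% progressed or dead. Ramipril: 15%, 40%, 45%.

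- Response difference: 15% − 15% = 0. A two-sided 5% test flags harm only at its false-positive rate of 2.5% in that direction.
- Progression or death: power = Φ(d/SE − 1.96), with SE = √(0.45·0.55/75 + 0.30·0.70/n₀).
  - n₀ = 100: SE = √(0.0033 + 0.0021) = 0.0735; 0.15/0.0735 − 1.96 = 0.08; power 0.53.
  - n₀ = 200: SE = 0.0660; power 0.62.
  - n₀ = 300: SE = 0.0632; power 0.66.
- For 50% against 30%, the same formula gives 0.77, 0.86 and 0.88.

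**Case 2: some responders are lost as well.** Controls: 20% response, 60% stable, 20% progressed. Here the null variance is pooled:

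power = Φ((d − 1.96·SE₀)/SE₁), with SE₀ = √(p̄(1−p̄)(1/75 + 1/n₀)), p̄ = (75p₁ + n₀p₀)/(75 + n₀), and SE₁ the unpooled standard error.

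Worked at n₀ = 75:

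- Response 15% against 20%: p̄ = 0.175, SE₀ = 0.0620, SE₁ = 0.0619; (0.05 − 0.1216)/0.0619 = −1.16; power 0.12.
- Progression 40% against 20%: p̄ = 0.30, SE₀ = 0.0748, SE₁ = 0.0730; (0.20 − 0.1467)/0.0730 = 0.73; power 0.77.

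| Ramipril response/stable/progression | Comparison | n₀ = 75 | 150 | 300 | 450 |
|---|---|---|---|---|---|
| 15/45/40 | response 15% v 20% | 0.12 | 0.14 | 0.15 | 0.15 |
| 15/45/40 | progression 40% v 20% | 0.77 | 0.88 | 0.93 | 0.95 |
| 10/50/40 | response 10% v 20% | 0.40 | 0.47 | 0.53 | 0.55 |
| 10/50/40 | progression 40% v 20% | 0.77 | 0.88 | 0.93 | 0.95 |
| 15/55/30 | response 15% v 20% | 0.12 | 0.14 | 0.15 | 0.15 |
| 15/55/30 | progression 30% v 20% | 0.29 | 0.39 | 0.47 | 0.50 |

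**What a progression comparison could exclude.** With 30% progressed or dead in both groups, the 95% half-width is 1.96·√(0.30·0.70·(1/75 + 1/n₀)): 0.137 at n₀ = 100 and 0.116 at n₀ = 300. Even with identical observed rates, the interval excludes only an excess above about 12 to 14 percentage points.

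**The case against.** - **Response rate is not defined.** Section 7.3 uses tumour response as the label for all three categories, "i.e. response, progression or stable disease", so the summary at each timepoint could be a tabulation by category that includes progression. This stands as a limit: the two-way split is the ordinary meaning, not the written one. If a tabulation by category is intended, Sections 12.4 and 12.7 need to say so.
- **The check is not blind to all progression.** A reader might infer that earlier progression would leave the response rate untouched. That is true only when every extra progressor would otherwise have been stable. Response is summarised at each timepoint, so responders who progress by Week 22, or patients who progress instead of responding, lower the rate. If the extra 15 points in Case 1 came proportionally from responders and stable patients, response would fall from 15% to 15 × 55/70 = 11.8%. The criticism is then low power, not blindness.
- **The forms do not date progression as such.** They date leaving agent or study, and progression is a permitted reason rather than a mandatory trigger. This stands; progression has to come from the scan assessments.
- **Other evidence and oversight exist.** Section 2.2 cites preclinical work showing no protection of tumour. Section 6.1 cites 160 GBM patients whose survival did not differ by ACE-inhibitor treatment. Deaths are reported, and Section 11.4 lists patient status and adverse events among the matters the DSMB may review. This lowers the prior concern, but none of it is a planned comparison of progression or death with controls.
- **The replacement has limits too.** Scheduled scans after baseline are only at Weeks 10 and 22. Optune may start after the Week 10 assessment, and Section 3 cites longer survival with it. Patients may leave the study at progression, so later deaths can be missed. Power for a 15-point excess was only 0.53 to 0.66. All of this stands and narrows the fix.

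**Conclusion.** The concern holds in a limited form. Response rate is the only measure named for the tumour-protection question, while progression and death are collected and not analysed for it. On the ordinary reading of response rate, the check cannot detect a shift from stable disease to progression, or its timing. In the assumed cases where response also falls by 5 to 10 points, its power is 12 to 55%, against 77 to 95% for progression when progression doubles from 20% to 40%. When progression rises only from 20% to 30%, both are weak (12 to 15% and 29 to 50%). These figures rest on assumed rates and control sizes and on all 75 patients being assessed.

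Two stronger readings are not supported. One is that a flawed tumour comparison would decide whether the randomised trial starts: Section 1.1.1 ties that decision to retention, and Section 12.2 uses the cognitive effect size and dropout to power and assess the later study. The other is that analysing progression would settle the matter: a half-width of about 12 to 14 points does not rule out tumour protection. The Section 8.2 sentence is not itself in error; the gap lies in Sections 12.4 and 12.7.

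**What to change.** 1. In Sections 12.4 and 12.7, define the response rate: which categories count, at which visit, and over which patients.
2. In the same sections, add the proportion progressed or dead by Week 10 and by Week 22 among all patients who took at least one dose of Ramipril. Give the difference from the RTOG 0825 control arm with a 95% interval, and state how patients who leave the study before Week 22 are counted.
3. Add progression to objective 1.2.5, and keep the response rate as a supporting measure.
4. In Section 12.7, replace the rule-out wording with a report of the size of excess progression or death that the interval excludes.
5. State the limits: treating-physician assessment, possible radiation effect at the 1-month scan, Optune use after Week 10, off-study exit at progression, scheduled scans only at Weeks 10 and 22, and a non-randomised comparator.

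The cost is SAP wording and one added table. No new visits or scans are needed. Section 2.3 says access to the RTOG 0825 data is agreed; the sponsor should confirm that they include progression and death data comparable in definition and timing, which the documents do not show.
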